APPENDIX

- I Patient information sheet and informed consent**
- II Knee society score evaluation (KSS)**
- III WOMAC patient questionnaire,
EQ-5D patient questionnaire,
Visual Analogue Scale (VAS) as patient questionnaire to measure results of chair raise test**
- IV and V Product Information**

SCORPIO PS Vs SCORPIO NRG PS

Comparative Investigation of Function

STUDY DESIGN SUMMARY

- **Surveillance design:** Single-centre, prospective, randomized comparative study.
- **Objectives:** To compare the average Range of Motion and Chair Raise achievement ratios. All complications will be documented.
- **Regulatory status:** Scorpio PS: CE Number: 0050
Scorpio PS NRG: CE Number :0086
- **Number of subjects to be enrolled:** All consecutive Scorpio patients are included until a group size of 88 is reached.
- **Clinical evaluations:** Chair raise test, Stair climb test, WOMAC patient self-evaluation, EQ-5D patient questionnaire. Standard clinical, functional and pain parameters (Knee Society Score), pre-operatively and post-operatively. All per- and post-op complications.

SCORPIO PS Vs SCORPIO NRG PS

Comparative Investigation of Function

1 INTRODUCTION

The Scorpio TKA family offers a complete range of Fixed Bearing, Mobile Bearing and revision components, all of which share a single design philosophy. Central to this philosophy is one idea incorporating a single M/L and A/P axis design, supported by a single instrument platform. In an otherwise satisfactory total knee arthroplasty (TKA) (well aligned, well fixed, stable, and with good flexion), symptoms related to extensor mechanism function and the patellofemoral articulation, including anterior knee pain, are the prevalent issues after TKA^{1,3,13}. Many factors influence the outcome of TKA, including prosthetic design. Classic kinematics theory teaches that knee flexion and extension occurs around changing instant centers of rotation. Several reports indicate that TKA's with a multiradius sagittal profile do not restore extensor mechanism moment arms to normal, with the greatest reduction occurring in the last 30 degrees of extension^{5,9}. The validity of the anatomic observations that are the foundation for the changing instant centers of rotation has been challenged.¹¹ Other anatomic studies⁴ indicate that knee motion occurs around a single, fixed flexion-extension axis located in the posterior condyles. This single flexion extension axis is approximated by the transepicondylar axis.² The relatively anterior axis of rotation in multiradius TKA's may account, at least in part, for why extensor mechanism moment arms are shorter after TKA. All other factors being equal, a relatively posterior flexion-extension axis would lengthen the extensor mechanism moment arms and improve extensor mechanism function. Several studies have proved the functional benefit from this improved moment arm. The Scorpio NRG has a redesigned tibial insert, and improved Post and Cam design. Also the posterior condyle height of the femoral component is reduced. These improvements should reduce the operation time, decrease the post operative ventral knee pain, improve rotation in deep flexion and increase maximum flexion. The Standard procedure at the academic hospital Maastricht consists of implantation of the Scorpio PS knee prosthesis, the same prosthesis that will be used in the control group of this study. If a patient's anatomy or specific lifestyle functions require a non scorpio prosthesis, it is possible to implant a NEXgen total knee prosthesis. This category of patients will not be asked to participate in this study.

The purpose of this investigation is to primarily compare the post-op function recovery of and complications of patients who received a Scorpio PS or Scorpio NRG PS design. A secondary purpose is to compare anterior knee pain, patella tracking and patella tilting between these two groups.

2 STUDY DESIGN

This is a prospective single-centre post market randomized comparative study.

2.1 *Pre-operative inclusion*

Patients on the waiting list for a total knee prosthesis who fulfil the inclusion and exclusion criteria will be asked to participate in this study. Oral and written information (appendix 1)

about the study will be given to the patient at the first hospital visit, related to the TKP. Oral information will be given again at a pre-operative information meeting one week before surgery. All study information will be given by the scientific researcher and orthopaedic surgeon. When a patient wants to participate the informed consent (appendix 1) will be signed and all pre-operative study information will be completed. This consists of demographics, medical history, a knee society score evaluation (KSS) (appendix 2), a stair climb and chair raise test combined with a VAS (visual analogue scale, appendix 3) score to measure pain. The VAS score is a 10 point scale with zero as no pain and 10 as the worst possible pain. A WOMAC patient questionnaire (appendix 3) and EQ-5D patient questionnaire on health status (appendix 3) will be done and additional X-rays will be made to measure pre-operative patella tracking and tilting.

2.2 Randomisation procedure

The randomisation procedure will be executed by the scientific researcher with the computer programme randomizer. After defining group size and the amount of subgroups, a list will be given with patient inclusion number and the prosthesis that has to be used. The scientific researcher will make envelopes with a form inside which mentions the patient inclusion number and type of prosthesis that has to be implanted. On the day of surgery a randomisation envelope will be opened.

If the surgeon notices during the operation that the study prosthesis is not suitable for the patient's anatomy, he will exclude the patient from the study and will place a suitable prosthesis.

The following criteria determine deviation from the randomisation procedure:

- Bone stock quality far less than expected by X-ray (patient will receive long stem revision prosthesis and will be excluded from the study)
- Fracture or fissure in tibial plateau threatening prosthesis stability (patient will receive long stem revision prosthesis and will be excluded from the study)

This will be mentioned in the CRF as a complication and the patient will be excluded from further participation.

The patient will not be informed which prosthesis he/she has received.

All study related operations will be performed under computer navigation.

2.3 post-operative evaluations

After surgery the patient will be evaluated at fixed follow up moments (Table 2 page 8). At each follow up moment a KSS evaluation, a chair raise and stair climb test combined with VAS pain score will be done. Also patient questionnaires (WOMAC, EQ-5D) will be done and X-rays will be taken.

The KSS score consists of a knee score (pain, range of motion en function of the prosthesis) and a function score (walking, stair climbing, use of support). To compare this KSS between

the different follow up moments the improvement can be measured. The stair climb and chair raise test will be executed in the same way at every follow up. The pain during these two activities measured with a VAS will be compared between the follow up moments.

All clinical measurements will be done by the clinical researcher. Specific knee clinical evaluations have to be done by a knee specialist to make sure that everything is done correctly.

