6 SELECTION OF PATIENTS

6.1 *Number of patients*

The number of patients is based on average postoperative flexion as the primary endpoint. According to Morawa¹⁰ Scorpio patients showed a maximum post-operative flexion of 104 degrees. An increase in maximum flexion of 5 degrees is already noticeable for the patient, so clinically important. According to pre marketing results the Scorpio NRG PS knee prosthesis can reach a flexion of more than ten degrees extra compared to the Scorpio PS. For the primary endpoint we want to aim at an increase in maximum flexion of 7 degrees. According to Schouten¹² a sample size of 40 patients in each group is needed with a difference in flexion of 7 degrees, a standard deviation of 11^{7,8} a 80% power with a significance level (alpha) of 0.05 (two-tailed). When we take into account a lost of FU of 10% a total groupsize of 88 is anticipated.

6.2 *Patient selection criteria*

All patients on the waiting list for a total knee prosthesis at the department of orthopaedics at the AZM will be checked for suitability for this study. Patients will be verbally and in writing informed about the study during the first visit related to the TKP, and will be provided with the patient information. One week before surgery during a pre-operative visit the patients will be orally informed again, All questions about the study will be answered and the patient will be asked to participate in this study. If a completely informed patient wants to participate, the informed consent will be signed.

If a patient doesn't want to participate it is very likely that he will receive the Scorpio PS prosthesis since this is the standard used knee prosthesis at the AZM. If a patient does or doesn't want to participate has no effect on day of surgery or further medical care.

The confidentiality of the subject will be maintained at all times. The patient will be told that he/she is free to refuse the collection of his/her clinical data or to withdraw from the Investigation at any time without compromising future medical care.

TABLE 1. Patient Inclusion and Exclusion Criteria

Inclusions

- Patients requiring a primary TKA
- Male and nonpregnant female patients
- Between 18 and 80 years of age at time of surgery
- Patients with a diagnosis of osteoarthritis (OA), avascular necrosis (AVN), and not severe posttraumatic arthritis
- No previous osteosynthesis of the involved knee during the last 12 months

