17 ETHICAL CONSIDERATIONS

Informed Consent

Prior to entry into the Surveillance the investigator (or nominated representative) will give the patient written (in native language of the patient) and verbal explanation of the nature of the study to an appropriate level of detail. The patient must give a written consent to participate in the study. Patients are invited to sign and date the consent form, indicating their consent for enrolment (Investigators may not date the consent form on the patient's behalf).

The investigator (or nominated representative) will also sign and date the Consent Form to indicate that the purpose, risks and benefits of the study were explained to the patient and their signature witnessed. The original signed Consent Form will be filed at the Investigational site.

Patients are free to withdraw from the Investigation at any time and are under no obligation to provide a reason for doing so. A clinical trial insurance and a liability insurance is arranged. An independent orthopaedic surgeon is appointed who is fully informed about this study but does not participate in the study.

Patients can, at any time, receive information about his/ her results.

The study will be performed according to the declaration of Helsinki, wet medisch-wetenschappelijk onderzoek met mensen and guidelines CCMO.

Stryker's local CRA will provide the MEC azM/UM with the following reports:

- An annual progress report
- An end-report, sent within 8 weeks after completion of the study
- An end-report containing the results and conclusions, sent within 1 year after completion of the study

Personal data protection

Stryker Europe affirms and upholds the principle of the patient rights to protection against invasion of privacy. All data recorded in the CRFs or used for further evaluation are coded by patient study number. Identification is restricted to authorized persons. In all data analyses the identity of patients will remain anonymous. Anonymous patient data may be stored and electronically processed by Stryker Europe for the purpose of scientific evaluation and may be forwarded to a company and/or an authority located in- and outside Europe for registration and/or marketing purposes. Only authorized representatives of Stryker Europe and health authorities will have allowed access to personal medical records for the sole purpose of checking the accuracy of data collected in the trial.

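### The role that makes the allocation list and envelopes also informs candidates before consent, so nothing prevents foreknowledge of assignment; separately, Section 2.3 conflicts with Sections 4 and 9.1.4 on who measures post-operative flexion

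*Combined protocol and SAP*

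**What the plan says.** **Allocation.** Section 2.2 states: "The randomisation procedure will be executed by the scientific researcher with the computer programme randomizer". Once group size and number of subgroups are set, "a list will be given with patient inclusion number and the prosthesis that has to be used". It continues: "The scientific researcher will make envelopes with a form inside which mentions the patient inclusion number and type of prosthesis". Then: "On the day of surgery a randomisation envelope will be opened". It does not say who opens the envelope, who assigns inclusion numbers or when, or whether the envelopes are sealed, opaque and used in sequence.

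**Recruitment.** Section 2.1 states: "All study information will be given by the scientific researcher and orthopaedic surgeon". That includes the meeting one week before surgery. Section 17 says that "the investigator (or nominated representative) will give the patient written (in native language of the patient) and verbal explanation" before entry. The study design summary says: "All consecutive Scorpio patients are included until a group size of 88 is reached". Section 6.2 adds that whether patients "want to participate has no effect on day of surgery or further medical care".

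**Who measures flexion.** Section 3 makes maximum flexion, active and passive, at every clinical follow-up the primary objective. Section 4 has a physiotherapist measure it and states that this person is blinded, as the patient is. Section 9.1.4 lists active and passive range of motion under the physiotherapist. Section 2.3, headed as post-operative evaluations, gives every clinical measurement to the clinical researcher and then requires a knee specialist for specific knee evaluations. It describes the Knee Society Score as including range of motion and does not mention blinding. Section 9.1.3 gives active range of motion at discharge to the clinical researcher.

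**The concern.** Concealment protects a randomised comparison up to the moment a patient is irrevocably enrolled. If someone who talks to candidates can work out the next prosthesis, encouragement or discouragement can depend on it, and the groups may then differ in prognosis in either direction. The baseline tables in Section 14.1, together with the pre-operative range of motion, would show imbalance in what is measured. They would not show the rest, and the t-test named in Section 14.1 adjusts for nothing.

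The assessor question is different in kind. A goniometer reading involves judgement, and the primary hypothesis has a direction (NRG higher by at least 7 degrees). If a site followed Section 2.3, the blinding stated in Section 4 would not cover the person taking the primary reading. A drift in readings with knowledge of the implant could not be separated from a treatment effect afterwards.

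**Working it through.** **Allocation, step by step.**

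1. Who knows the link from number to prosthesis? Under Section 2.2, the scientific researcher, who runs the program, receives the list and fills the envelopes.
2. Who speaks to candidates before consent? Under Section 2.1, the scientific researcher and the orthopaedic surgeon; under Section 17, the investigator or a representative. Only the scientific researcher is in both groups. Nothing shows that the others see the list.
3. Does that role know a given candidate's assignment? Only if the role also knows which number that candidate will receive. The documents are silent on who gives out numbers, when, and whether in order of consent or of surgery. Foreknowledge is therefore neither established nor prevented.
4. What limits the opportunity? Opening on the day of surgery can conceal the assignment from the surgeon, but not from the person who filled the envelope. Consecutive enrolment restricts selection, but still depends on consent. The Section 6.2 statement means that participation does not alter the surgery date; it does not prevent encouraging or discouraging a candidate.

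No figure can be put on this part, because the documents give no basis for one.

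**Assessor, side by side.**

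| Section | Visit | Who measures | Blinding stated |
|---|---|---|---|
| 2.3 | post-operative | clinical researcher; knee specialist for specific knee evaluations | no |
| 4 | flexion within the Knee Society Score | physiotherapist | yes |
| 9.1.4 | 6 weeks to 5 years | physiotherapist | not repeated |
| 9.1.3 | discharge (active range of motion only) | clinical researcher | no |

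Sections 2.3 and 9.1.4 cover the same visits and the same measurement and name different roles. Discharge is a separate matter: Table 2 schedules no clinical and Knee Society Score evaluation there.

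**Illustration of a reading shift.** Inputs from Section 6.1 are SD 11, difference 7, two-sided alpha 0.05, power 80%, 40 per group and 88 in total.

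The plan's own figure first: n = 2 × (1.960 + 0.842)² × 11² / 7² = 38.8, so 39 per group by the normal formula. The t-test version gives 39.7, so 40. Then 80 × 1.10 = 88. Both stated figures reproduce. After 10% loss, 88 × 0.90 = 79.2, or about 40 per group.

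With 40 per group, SE = 11 × √(2/40) = 2.460, df = 78 and critical t = 1.9908. With no true difference and an assumed systematic shift d toward NRG, the chance of a significant result favouring NRG is the probability that a noncentral t with noncentrality d/2.460 exceeds 1.9908. With no loss, 44 per group, SE = 2.345, df = 86 and critical t = 1.9879.

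| Assumed shift (degrees) | 40 per group | 44 per group |
|---|---|---|
| 0 | 2.50% | 2.50% |
| 1 | 5.96% | 6.20% |
| 2 | 12.37% | 13.21% |
| 3 | 22.50% | 24.35% |

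The shifts are assumptions; the documents give none. The table concerns measurement only and says nothing about selection.

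**The case against.** On allocation, the fair reply is that a shared role is not the same as a known assignment. The list is keyed to inclusion numbers, and the plan does not say that the researcher knows which number a candidate will get. The surgeon and the investigator or representative also inform patients, enrolment is consecutive, and the envelope stays closed until surgery. This stands as a limit on what can be claimed. A reader might infer that allocation is unconcealed as a matter of fact, or that everyone who recruits can see it; the documents support neither. The silence on numbering is not a safeguard, however, and no other provision separates the list from recruitment. Silence about sealing and opacity is a lesser matter, since neither would hide the contents from the person who made the envelopes.

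On the assessor, it can be said that Section 4 speaks specifically to flexion, that Section 9.1.4 agrees with it, and that one general sentence in Section 2.3 should yield. That is probably what was meant. Still, the knee-specialist sentence does not name the physiotherapist and so adds a third role, and a protocol should not leave the reader of its primary endpoint to interpretation.

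Three stronger inferences fail. The plan does not lack assessor blinding: Section 4 states it, and Section 2.3 is silent rather than contrary on blinding itself. Section 9.1.1 is not clearly contradicted, because it is pre-operative and Section 2.3 is headed post-operative. And the documents do not say that the scientific researcher and the clinical researcher are the same person, so the two parts cannot be joined into one claim about a person who knows the allocation and measures the outcome.

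**Conclusion.** Both parts hold and should be corrected. The first is an unprevented risk of selection bias, confined to one of the roles that inform candidates, of unknown size and direction and only partly limited by the other provisions. It is not evidence that steering would occur. The second is a contradiction between Section 2.3 and Sections 4 and 9.1.4 on who takes the primary measurement after surgery.

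That the roles overlap and that the sections conflict follows directly from the text. The consequences are conditional: on how inclusion numbers are assigned for the first part, and on which section a site follows for the second. The percentages show only how sensitive the test would be to a shift of 1 to 3 degrees if one existed; a reader should not take them as estimated error rates for this trial, and the conclusion does not rest on them. Sample size, alpha and nominal power are unaffected.

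**What to change.** **Section 2.2.** Have someone already on the study or sponsor team, with no part in recruitment or outcome measurement, generate and hold the list and prepare sequentially numbered, sealed, opaque envelopes. State who assigns inclusion numbers and when. The scientific researcher can go on informing patients. The cost is revised wording and a one-time handover of one 88-patient list, with that person available to keep it.

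**Section 2.3.** Amend it so that flexion at every follow-up visit from 6 weeks to 5 years is measured by the blinded physiotherapist of Section 4, without access to the allocation list or operative notes. State that the discharge range of motion taken by the clinical researcher under Section 9.1.3 does not feed the primary endpoint. The cost is wording only, since Section 9.1.4 already places the physiotherapist at these visits.

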4 METHODS

Performance will be clinically measured using the Knee Society Score (Ewald, 1989; appendix 2). As part of the KSS flexion will be measured, both passive and active. The measurement will be done by a physiotherapist. Like the patient the physiotherapist will be blinded for the treatment.

The Chair Raise test(standing up from a firm straight-backed chair keeping the arms folded across the chest) and stair climb test(ascending a flight of eleven 17.8 cm tall steps with an 30 cm tread depth, use of one hand rail is allowed) is combined with a 10 point VAS measurement of anterior knee pain(McCormack et al., 1988). This consists of a pain scale from 0 to 10 on which the patient can point to the amount of pain (0 means no pain, 10 means the worst possible pain) Recording of the nature and incidence of all intra-operative and post-operative complications will be the method to assess safety. The difference between computer navigation measurements of leg axis and range of motion and clinical and X-ray measurements of these parameters will be evaluated. For this evaluation the pre-op standard X-rays and the per-operative computer navigation data will be used.

The relation between patella tilting and post-operative pain will be measured during functional tests Stair climb and chair raise according to a Visual analog scale (VAS) .

Patellar tilting will also be assessed on consecutive X-rays by the orthopaedic surgeon.

A WOMAC patient questionnaire (appendix 3) will be done to evaluate the patient's opinion on recovery, post-operative pain, and function(Bellamy et al., 1988).

An EQ-5D patient questionnaire (appendix 3) will be done to evaluate the patient's opinion of their health status (mobility, self-care, usual activities, pain/discomfort, anxiety/depression and a visual analog scale (VAS) to measure the patient's self-rated health outcome).

All evaluations will be conducted on the follow up moments mentioned in the follow up table

at page 8.

The prostheses used in this study both have a CE mark. All information concerning these prostheses is attached as appendix 4

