11 PATIENT WITHDRAWALS

Every attempt must be made to ensure that all the patients return for all of the post-operative assessments. However, patients are free to withdraw from the Investigation at any time and are under no obligation to provide a reason for doing so. Patients who withdraw from the Investigation should have the reason for their withdrawal recorded on the case report forms (CRF's), if at all possible. All attempts should be made to ascertain whether any patient apparently lost to follow up has actually chosen not to return or is deceased.

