12 REPORTING OF RESULTS

All the above-mentioned pre-operative patient assessments, per-operative details and post-operative follow-up assessments will be recorded on the CRFs (Case Record Forms), which will be provided, and also in a database.

A case record form will be completed for each patient.

All data recorded in the CRFs should be in agreement with the information reported in the patient's hospital records and other primary sources of data.

In order to maintain patient confidentiality, the patient's name or address will not be recorded on the form. Only the patient's study number will be recorded on the CRF. For means of tracing the patient the scientific researcher has a code list on which patient study number and his name, date of birth and patient hospital number is mentioned.

These case record forms must be completed, checked for accuracy and signed by the investigator.

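### Randomised patients taken out of the study during surgery are no longer followed, so their later complications and revisions are lost to the safety comparison; the flexion comparison is biased only if the number or kind of such patients differs by arm

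*Combined protocol and SAP*

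**What the plan says.** Section 2.2 fixes the order of events. Allocation is revealed first: "On the day of surgery a randomisation envelope will be opened", and the form inside names the prosthesis. If the surgeon then finds during the operation that the study prosthesis does not fit the anatomy, "he will exclude the patient from the study and will place a suitable prosthesis". Two criteria follow: bone stock much poorer than the X-ray suggested, and a tibial plateau fracture or fissure that endangers stability. Section 2.2 then says: "This will be mentioned in the CRF as a complication and the patient will be excluded from further participation".

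Section 4 describes the patient and the physiotherapist as blinded. The surgeon is not so described, and has to know which device to implant.

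On safety, Section 4 states: "Recording of the nature and incidence of all intra-operative and post-operative complications will be the method to assess safety". The study design summary adds: "All complications will be documented". Section 3 sets a secondary hypothesis of no difference in complications, and Section 14.1 lists revisions and removals among the comparisons.

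Section 14.1 compares groups by Student's t-test and names no analysis set. The purpose at the end of Section 1 is worded by implant: "patients who received a Scorpio PS or Scorpio NRG PS design". Section 11 says: "Every attempt must be made to ensure that all the patients return for all of the post-operative assessments", but it deals with voluntary withdrawal and loss to follow-up.

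**The concern.** The exclusion happens after randomisation, is decided by someone who knows the arm, and ends data collection. Two things are at stake.

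- **Safety.** A patient with an intra-operative fracture or fissure has already had a surgical complication. Section 2.2 stops observation there, so any later complication or revision goes uncounted. Section 16.1 lists tibial fracture during implantation as a risk, and says that the expected absence of extra risk with the NRG has yet to be proven. If such events were commoner with one design, their consequences would be missing from that arm, and the difference in later complications would be understated.
- **Flexion.** The patients left in each arm are comparable only if the rule removes the same share and the same kind of patient from both. If it does not, mean flexion in the retained groups differs for reasons unrelated to the implant.

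The number of exclusions by arm can be rebuilt from the CRF and the randomisation list. The later outcomes cannot, because they are never collected.

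**Working it through.** **The plan's own figure (Section 6.1).** Inputs: difference 7 degrees, SD 11, 80% power, two-sided alpha 0.05. By the normal formula, n = 2 × (1.960 + 0.842)² × 11² / 7² = 38.8, so 39 per arm. The t-based version gives 39.7, so 40, as stated. Then 80 × 1.10 = 88. The sample size reproduces. Its 10% allowance is for loss to follow-up and does not mention intra-operative exclusions.

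**When retained patients are compared with bias.** Let e be the share excluded in an arm, and D the amount by which the excluded patients' expected flexion lies below that of all patients randomised to that arm. Then

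bias = D_N × e_N/(1 − e_N) − D_C × e_C/(1 − e_C), with N for NRG and C for control.

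The values of e and D below are assumed, because the documents give none.

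- Same share and same kind (5% in each arm, D = 11 in both): 0.0 degrees.
- 5% in one arm only, D = 11: 11 × 0.05/0.95 = 0.58 degrees.
- 5% in each arm but different kinds (D = 11 against 0): 0.58 degrees. With D = 11 against −11: 1.16 degrees.

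Equal counts therefore do not guarantee an unbiased comparison. The kind of patient matters as well.

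**Size with a few excess exclusions.** Suppose k low-flexion patients of 44 are excluded in one arm while their counterparts stay in the other, with flexion 15 to 20 degrees lower. The shift is (k/44) × deficit. Two-sided rejection with no implant effect comes from the noncentral t (SD 11, 40 per arm, 78 df).

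| k | Deficit | Shift (degrees) | Rejection |
|---|---|---|---|
| 1 | 15 | 0.34 | 5.2% |
| 1 | 20 | 0.45 | 5.4% |
| 2 | 15 | 0.68 | 5.9% |
| 2 | 20 | 0.91 | 6.5% |
| 4 | 20 | 1.82 | 11.3% |

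The formula holds the SD at 11. In simulation, the low-flexion patients kept in the other arm widen the SD, and the rates fall to 5.1%–6.2% for k = 1 or 2, and to 9.6% for k = 4 with a 20-degree deficit. When such patients are excluded in both arms alike, rejection stays at 4.9%–5.1%.

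**Safety.** With 1 or 2 patients of 44 unobserved, the share of an arm with a later complication is understated by at most 1/44 = 2.3 or 2/44 = 4.5 percentage points. That ceiling is reached only if every one of them has a later complication.

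**What an as-randomised flexion analysis would cost.** Assume knees without a study prosthesis flex 15 or 20 degrees less than the Scorpio PS mean in either arm, with 44 per arm and 10% random loss. Simulated power at a true 7 degrees among recipients is:

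| Such patients per arm | As randomised (deficit 15 / 20) | Recipients only (deficit 15 / 20) |
|---|---|---|
| 0 | 79.8% | 79.8% |
| 1 | 75.8% / 74.8% | 78.9% / 78.9% |
| 2 | 71.8% / 69.5% | 77.8% / 77.9% |

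**The case against.** The strongest reply has four parts.

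1. *The surgeon's discretion is narrow.* A reader might infer an open-ended power to drop patients from the general sentence about anatomy. The text does not clearly support that. The sentence introducing the list says that those criteria settle when randomisation is departed from, and only two are given. Both concern bone, and both lead to the same type of replacement implant in either arm. Section 16.1 calls the two designs basically the same. This stands and makes selective exclusion less likely. It does not remove it: how poor the bone is, and whether a fissure endangers stability, are still judged by someone who knows the arm.
2. *The harm is not hidden.* A reader might infer that an implant-related fracture disappears from the results. It does not. Section 2.2 enters it in the CRF as a complication, Section 9.2 provides for intra-operative complications, and nothing removes it from the Section 14.1 tables. This stands. What is lost is what happens afterwards.
3. *The purpose concerns recipients of the two designs.* A patient given another implant received neither, so ending follow-up fits that purpose. This is a fair argument for a recipients-only flexion analysis. It is weaker for safety, where Section 4 speaks of all complications and where a fracture during implantation may itself result from the assigned device.
4. *The sizes are assumed, and the remedy costs power.* Both are true. The power cost is a reason to choose the primary flexion analysis deliberately. It is no reason to stop collecting the data.

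**Conclusion.** The point holds as a defect in follow-up and in the definition of the analysis, and it should be fixed. Section 2.2 ends observation of some randomised patients, Section 11 does not reverse this, and the result conflicts with the safety method in Section 4.

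It would be going too far to say that the rule biases the flexion result or seriously inflates its error rate. Bias needs a difference between arms in the number or kind of patients excluded. The documents do not show one, and they give neither an exclusion rate nor a flexion deficit. With 1 or 2 excess exclusions of 44 and an assumed deficit of 15 to 20 degrees, the shift is 0.3 to 0.9 degrees and rejection is at most about 6.5%. The 11.3% figure needs four exclusions in one arm, none in the other, and the largest assumed deficit.

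Even when exclusion is alike in both arms, the as-randomised effect differs from the effect among recipients: if 5% in each arm get the same other implant with the same result, 7 × 0.95 = 6.65 degrees. That is a difference of target and not a bias, but it is why the plan must say which effect it estimates. The main loss is in the safety comparison, and it cannot be repaired at analysis. Confidence is medium, because the size rests on assumptions.

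**What to change.** Leave the surgeon's choice of implant unchanged.

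- **Section 2.2:** wherever the text ends study participation for these patients (the general sentence, both listed criteria and the closing sentence), write instead: *remains in scheduled follow-up, where consent allows*.
- **Section 14.1, safety:** add *Complications and revisions are analysed as randomised, and the intra-operative event is counted in the assigned arm. Intra-operative deviations are reported by assigned arm, with reasons.*
- **Section 14.1, flexion:** before data are seen, name one analysis as primary and report the other as a sensitivity analysis. The candidates are as randomised, or among recipients of one of the two study designs, which matches the stated purpose. Two unranked tests of the primary endpoint should not be left open.

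**Cost.** Wording in two sections and scheduled visits for a few patients. The consent pages were not available for review; if consent does not cover follow-up after a deviation, one sentence is needed there. If as-randomised flexion is primary, the plan should state the power cost under the assumed deficits: about 75%–76% with one such patient per arm, or 70%–72% with two. The change has to be made before or early in enrolment, since visits not made cannot be recovered.
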